## **4. ANALYSIS SETS**

### **4.1 Safety Analysis Set**

The primary analysis population for safety will be the safety analysis set, which will include all randomized subjects who received investigational product. For all safety analyses, subjects will be analyzed according to the treatment they actually received.

## **5. STUDY PATIENTS**

### **5.1 Disposition of Patients**

The disposition of subjects will be summarized for all subjects screened in the study. The following disposition information will be summarized overall for each study part, and for the study overall:

- The number and percentage of subjects that were screened, randomized, that were screen failures, and the reason for screen failure

The following disposition information will be summarized for the safety analysis set for each study part by dose group, and for the study overall by pooled treatment group:

- The number and percentage of subjects who completed the study
- The number and percentage of subjects who discontinued the study and the reason for premature discontinuation

A data listing of subject disposition for all subjects in the safety analysis set and a data listing of screen failures for all screened subjects will also be provided.

A data listing of visits not done, or completed as a home health visit or telephone visit as a replacement for a scheduled in-clinic visit and the corresponding reason for all subjects in the safety analysis set will be provided.

### **5.2 Protocol Deviations**

Protocol deviations for all subjects in the safety analysis set will be summarized for each study part by type and dose group. A data listing of all protocol deviations for all subjects in the safety analysis set will also be provided.

## **6. DEMOGRAPHIC AND OTHER BASELINE CHARACTERISTICS**

Subject demographics and other baseline characteristics will be summarized descriptively for the safety analysis set for each study part, and for the study overall by pooled treatment group. The demographic and baseline characteristic summaries will be used to describe the study population.

Demographic data will include age, sex, race, ethnicity, baseline percent predicted FEV1, concomitant CFTR modulator use, and genotype. Genotype will be summarized by first mutation class and second mutation class (e.g., ‘Class I/Class II’). Age (years) will be calculated using the date of birth and the date of informed consent, as described in Section 3.

Medical history will be coded using the Medical Dictionary for Regulatory Activities (MedDRA) Version 23.1 to identify the system organ class and preferred term. A summary table will be presented by dose group to reflect a count of medical history events occurring in subjects in the safety analysis set within each system organ class and preferred term for each study part, and for the study overall. All percentages will use the number of subjects in the safety analysis set as the denominator. Therefore, if a subject has more than 1 medical history event within a system organ class, the subject will be counted only once in that system organ class. If a subject has more than 1 medical history event that codes to the same preferred term, the subject will be counted only once for that preferred term. Tabular summaries will be sorted by overall (MRT5005 + Placebo) descending frequency by system organ class and by preferred term.

Individual data for demographics and medical history will be presented in the data listings for subjects in the safety analysis set.

## **7. MEASUREMENTS OF TREATMENT COMPLIANCE**

Treatment compliance and exposure to investigational product will be summarized in terms of number of doses (total, full, and partial) administered. The number and percentage of subjects with 1, 2, 3, 4, or 5 total doses (sum of full and partial) administered will be presented by dose group for each study part, and by pooled treatment group for the study overall. The number of full doses and partial doses administered will be separately summarized continuously using descriptive statistics by dose group for each study part, and by pooled treatment group for the study overall. The number of full doses administered is the number of individual occurrences (days) for which a subject received a full dose of investigational product based on the completion of nebulization for the expected number of medication chambers, even if there was excess residual observed in the chamber after completion of nebulization. A partial dose refers to incomplete nebulization. Full and partial doses are independent of the presence or absence of excess residual in the medication chamber.

Individual data for dosing, including the start and end dates and time of nebulization along with assessments of whether nebulization was complete and whether excess residual was present in the medication chamber will be listed by visit and nebulizer for subjects in the safety analysis set. The number of full doses and partial doses administered for each subject will be presented in a data listing for subjects in the safety analysis set. The following individual data for dosing for each subject at each visit will be presented in a data listing for subjects in the safety analysis set: date of IP administration, whether full dose was administered, reason if full dose not administered, actual number of medication chambers completed, and the expected number of medication chambers completed.

## **8. EFFICACY EVALUATION**

Not applicable.

## 9. SAFETY EVALUATION

### 9.1 Overview of Safety Analysis Methods

The safety analyses will be performed using the safety analysis set for the safety measures, which include extent of drug exposure, adverse events (AEs), vital signs, clinical laboratory data, ECGs, pulse oximetry, chest x-rays, spirometry, physical examinations, concomitant medications, and serum inflammatory markers.

Safety data will not be imputed, except for partial dates, which will be imputed only for defining TEAEs and for the calculation of the duration of the AE. Completely missing dates will not be imputed and any AE with a completely missing date will be classified as a TEAE. Imputed dates will not be presented in data listings.

Partial dates will be imputed for the purposes of defining TEAEs as follows:

- For a missing start day where the month and year are present, the start day will be set to the first day of the month, unless 1) the first day of the month is before the date of first dose of study drug and the month and year are the same as the month and year of the date of first dose of study drug, and 2) the end date is on or after the date of first dose of study drug or the end date is completely missing, in which case the start day will be set to the first day of first dose of study drug.
- For a missing start day and month where the year is present, the start day and month will be set to January 1st, unless 1) January 1st is before the date of first dose of study drug and the year is the same as the year of the date of first dose of study drug, and 2) the end date is on or after the date of first dose of study drug or the end date is completely missing, in which case the start day and month will be set to that of the date of first dose of study drug.
- For a missing end day where the month and year are present, the end day will be set to the last day of the month, unless the month and year are the same as the month and year of the last contact date for the subject, in which case the end day will be set to that of the subject's last contact date.
- For a missing end day and month where the year is present, the end day and month will be set to the subject's last contact date, unless the year of the subject's last contact date is greater than the end year, in which case the end day and month will be set to December 31st.

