### 9.3 Adverse Events

Adverse events will be coded using the Medical Dictionary for Regulatory Activities (MedDRA) Version 23.1 to identify the system organ class and preferred term.

Treatment-emergent AEs are defined as events that are newly reported or reported to worsen in severity after the start of treatment. Adverse events that occur after the treatment start date, occur on the treatment start date with a time that is equal to or after treatment start time, or that have a missing AE start date will be categorized as treatment-emergent. Treatment-emergent AEs will be summarized for the safety analysis set.

For summaries of TEAEs by time interval, the categorizations for Part A will be: Overall, Study Day 1, 1 < Study Day ≤ 7, 1 ≤ Study Day ≤ 29, and Study Day > 29. The categorizations for Part B will be: Overall, Study Day 1, 1 < Study Day ≤ 7, 1 ≤ Study Day ≤ 36, 1 ≤ Study Day ≤ 57, and Study Day > 57. The categorizations for Part D will be: Overall, Study Day 1, 1 < Study Day ≤ 5, 1 ≤ Study Day ≤ 11, 1 ≤ Study Day ≤ 32, and Study Day > 32. The categorizations for the study overall will be: Overall, through 1 month post-dose (Day 29, Day 57, and Day 32 for Part A, Part B, and Part D, respectively), after 1 month post-dose (> Day 29, > Day 57, and > Day 32 for Part A, Part B, and Part D, respectively). Any TEAE with a completely missing start date will not be categorized into a specific time interval, but will be included in the Overall category.

Any dose limiting toxicities identified will be addressed in the clinical study report (CSR).

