#### ***9.6.3.4 Prior and Concomitant Medications and Procedures***

The prior and concomitant medications will be coded using the latest version of World Health Organization Drug Dictionary (WHO Drug) Global (2020-SEP) to identify the drug class and preferred drug name.

Concomitant medications will include all medications that started on or after day of first dose of the study drug or that stopped on or after day of first dose of study drug, including medications that are classified as ongoing. Prior medications will include all medications that started and stopped prior to the day of first dose of the study drug. Any medication with a missing stop date (i.e., day, month, and year are missing) will be classified as ongoing. For a medication with a missing start date, the medication will be classified as both a prior and concomitant medication unless the stop date is prior the date of first dose of study drug, in which case the medication will be classified as a prior medication. For medications with start date prior to the date of first dose of study drug and missing end date, the medication will be classified as both prior and concomitant. Medications with missing start and stop dates will be classified as prior and concomitant.

The number and percentage of subjects using prior medications, and separately concomitant medications, will be tabulated by Anatomical Therapeutic Chemical (ATC) level 1 term, ATC level 2 term, and preferred drug name for all subjects in the safety analysis set by study part and dose group, and also for the study overall. If a subject has more than 1 medication within an ATC level 1 term, the subject will be counted only once in that ATC level 1 term. Similarly, if a subject has more than 1 medication within an ATC level 2 term, the subject will be counted only once in that ATC level 2 term. If a subject has more than 1 medication that codes to the same preferred drug name, the subject will be counted only once for that preferred drug name. All percentages will use the number of subjects in the safety analysis set as the denominator. The tabular summaries will be sorted by overall (MRT5005 + Placebo) descending frequency by ATC level 1 term, ATC level 2 term, and preferred drug name.

Prior and concomitant medication data will also be presented in a data listing for subjects in the safety analysis set.

Concomitant surgical procedures will also be presented in a data listing for subjects in the safety analysis set.

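### SAP 9.1 and 9.3 count an AE with no start date as treatment-emergent even when its end date is known to be before first dose

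*SAP*

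**What the plan says.** Four places in the SAP bear on this.

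- Section 9.1, on missing dates: completely missing dates are not imputed, and "any AE with a completely missing date will be classified as a TEAE". The sentence does not say whether the missing date is the start or the end.
- Section 9.3, on classification: AEs that begin after treatment start are treatment-emergent, "or that have a missing AE start date will be categorized as treatment-emergent". The definition just before it reads: "Treatment-emergent AEs are defined as events that are newly reported or reported to worsen in severity after the start of treatment". On display, 9.3 adds: "Any TEAE with a completely missing start date will not be categorized into a specific time interval, but will be included in the Overall category".
- Section 9.1, on partial start dates: where the known part of the start date matches the period of first dose, the start is moved to the date of first dose only if "the end date is on or after the date of first dose of study drug or the end date is completely missing".
- Section 9.6.3.4, on medications with a missing start date: the record is both prior and concomitant, "unless the stop date is prior the date of first dose of study drug", in which case it is prior only.

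Protocol 8.1 collects all AEs from the signing of consent, and screening can begin on Day -28, so pre-dose AEs will be in the database.

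**The concern.** An event that is known to have ended before first dose cannot have begun or worsened after treatment started, whatever its start date. The missing-start rule nevertheless makes it a TEAE, because neither 9.1 nor 9.3 looks at the end date. The SAP uses exactly that check in two neighbouring rules and gives no reason for leaving it out here.

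TEAE frequency is a core part of the primary endpoint (SAP 2.2.1), and dose groups in Parts A and B have three active subjects each. A single misclassified record can therefore be visible in a headline percentage. The error need not be conservative either: a false TEAE on placebo raises the comparator rate.

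A second, smaller matter is that 9.1 and 9.3 describe the rule in different words. A programmer working from 9.1 alone could apply it to a missing end date as well.

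**Working it through.** The plan states no figure that depends on this rule, so the check has two steps: apply the rules to each date pattern, then size one misclassified subject.

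**Step 1: classification by date pattern.**

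| Start date | End date | SAP 9.1 | SAP 9.3 | What the dates support |
|---|---|---|---|---|
| Completely missing | Known, before first dose | TEAE | TEAE | Not treatment-emergent |
| Completely missing | On or after first dose, or missing | TEAE | TEAE | Unknown; TEAE is a reasonable default |
| Month and year of first dose, day missing | Known, before first dose | Start set to the 1st of the month, so before first dose | Not TEAE | Not treatment-emergent |
| Known, pre-dose, no worsening | Completely missing | TEAE only if read literally and alone | Not TEAE | Not treatment-emergent |

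Row 1 is the error. Rows 1 and 3 carry the same decisive information, an end before first dose, and get opposite answers. The record with the less complete start date is the one called treatment-emergent.

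Row 4 is a wording conflict. Section 9.3 restricts the rule to the start date, and 9.1 read as a whole agrees with it. The partial-start rules in 9.1 name a completely missing end date as one condition for moving the start to first dose. If a missing end date already made an AE a TEAE, that condition would do nothing for TEAE status. It would do nothing for duration either, since an AE with no end date has no calculable duration. Those are the only two uses that 9.1 allows for imputed dates.

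**Step 2: weight of one subject.** SAP 2.5 plans 3 active and 1 placebo subject in each dose group of Parts A and B, and 6 active and 2 placebo in Part D. Parts A and B have four dose groups each, and placebo is pooled within part. Percentages use the number in the safety analysis set. If the subject has no other TEAE of that term, the shift is 100 × 1/N points.

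| Column | N | Shift (points) |
|---|---|---|
| Part A or B, one active dose group | 3 | 33.3 |
| Part A or B, pooled placebo | 4 × 1 = 4 | 25.0 |
| Part D, active | 6 | 16.7 |
| Part D, placebo | 2 | 50.0 |
| All parts, pooled active | 12 + 12 + 6 = 30 | 3.3 |
| All parts, pooled placebo | 4 + 4 + 2 = 10 | 10.0 |

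**Where it would appear.** Under 9.3 these records enter the Overall category only. That includes the overall summary (Table 14.3.1.1) and the Overall page of the by-interval tables, but not the Day 1, first-week or one-month windows. The febrile and hypersensitivity summaries in 9.4 require onset within 24 hours after nebulization, which a record with no start date cannot be shown to meet.

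**The case against.** The strongest defence is that treating unknown onset as treatment-emergent is a deliberately cautious convention. It matches other defaults in the SAP table footnotes: missing severity is counted as severe and missing relationship as related. That argument holds for row 2 of the first table, where timing is unknown. It does not hold for row 1, where the end date settles the timing.

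A second defence is rarity, and this one stands. The record must lack the day, month and year of onset yet have an end date before dosing. A start known to the month or year falls under the partial-date rules, which do consult the end date. AEs are collected prospectively over a short screening period, and Protocol 9.2 has omissions queried. A misclassified record would also be open to inspection, because SAP 9.3.2 lists all AEs with a treatment-emergent flag.

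It could also be said that the definition in 9.3 speaks of events being reported, so a screening event first mentioned after dosing might qualify. The sentence that follows it sorts AEs by when they occur relative to treatment start, which rules that reading out.

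In the other direction, a reader might infer from the wording of 9.1 that every screening AE still ongoing at first dose becomes a TEAE because it has no end date. In a population with chronic symptoms that would be a large effect. The documents do not support it. Section 9.3 names the start date, and each of its specific intervals begins on or after Study Day 1, with only a missing start date excused from them. Protocol 8.1.1 also has worsening of a pre-treatment event recorded as a new AE, so the pre-dose record does not itself become treatment-emergent.

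**Conclusion.** Wrong as written, minor. Under both 9.1 and 9.3, an AE with a completely missing start date and a known end before first dose is classified as a TEAE, which contradicts the definition in 9.3 and departs from the SAP's own handling of partial start dates and medications. The difference between the two sections over which date is meant should be cleaned up, but 9.3 resolves it, and it is not evidence that ongoing pre-dose AEs will be counted.

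The size per subject runs from 3.3 points in pooled active to 50.0 points in Part D placebo. These figures assume planned group sizes and a subject with no other TEAE of the same term. The 33.3-point figure belongs to Part A and B active groups only. The number of affected records is not given and may be zero.

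**What to change.** In SAP 9.1, refer to a completely missing start date. In both 9.1 and 9.3, add to the missing-start rule: *unless the end date, including an imputed end date, is before the date of first dose; a missing end date alone does not make an AE treatment-emergent.*

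Using the imputed end date is safe. Section 9.1 sets a partial end date to the last day of the month or year, or to the last contact date, so an imputed end before first dose means the event had ended by then. Records with no start date and an end on or after the date of first dose, or no end date, keep the cautious default.

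The cost is a short wording change in two sections and one condition in the program that derives the TEAE flag. Listing the AEs with a completely missing start date would show at once whether any record is affected.

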### 9.2 Extent of Exposure

Extent of exposure and treatment compliance are described in Section 7.

### 9.3 Adverse Events

Adverse events will be coded using the Medical Dictionary for Regulatory Activities (MedDRA) Version 23.1 to identify the system organ class and preferred term.

Treatment-emergent AEs are defined as events that are newly reported or reported to worsen in severity after the start of treatment. Adverse events that occur after the treatment start date, occur on the treatment start date with a time that is equal to or after treatment start time, or that have a missing AE start date will be categorized as treatment-emergent. Treatment-emergent AEs will be summarized for the safety analysis set.

For summaries of TEAEs by time interval, the categorizations for Part A will be: Overall, Study Day 1, 1 < Study Day ≤ 7, 1 ≤ Study Day ≤ 29, and Study Day > 29. The categorizations for Part B will be: Overall, Study Day 1, 1 < Study Day ≤ 7, 1 ≤ Study Day ≤ 36, 1 ≤ Study Day ≤ 57, and Study Day > 57. The categorizations for Part D will be: Overall, Study Day 1, 1 < Study Day ≤ 5, 1 ≤ Study Day ≤ 11, 1 ≤ Study Day ≤ 32, and Study Day > 32. The categorizations for the study overall will be: Overall, through 1 month post-dose (Day 29, Day 57, and Day 32 for Part A, Part B, and Part D, respectively), after 1 month post-dose (> Day 29, > Day 57, and > Day 32 for Part A, Part B, and Part D, respectively). Any TEAE with a completely missing start date will not be categorized into a specific time interval, but will be included in the Overall category.

Any dose limiting toxicities identified will be addressed in the clinical study report (CSR).

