AE	Count	AE_F06b	[3]	If a subject experienced more than 1 adverse event, the subject was counted only once for the closest relationship to nebulization/treatment administration. AEs with missing relationships were classified as being Related to nebulization/treatment administration.

Data Type	Footnote Type	Code	Prefix	Footnote
AE	Count	AE_F06d	[5]	If a subject experienced more than 1 adverse event classified as a pulmonary exacerbation, the subject was only counted once in the 'All' row. Subjects with both an investigator-defined and a protocol-defined TEAE classified as a pulmonary exacerbation were counted once in each row, 'Investigator-Defined' and 'Protocol-Defined'.
AE	Count	AE_F07	[4]	If a subject experienced more than 1 adverse event, the subject was counted only once for the maximum severity. AEs with missing severities were counted as Severe.
AE	Count	AE_F07a	[2]	If a subject experienced more than 1 adverse event with a preferred term associated with the febrile reaction, the subject was counted only once for the maximum severity of any of the preferred terms contributing to the febrile reaction. AEs with missing severity were counted as Severe.
AE	Count	AE_F07b	[2]	If a subject experienced more than 1 hypersensitivity reaction, the subject was counted only once for the maximum severity of any of the hypersensitivity reactions. AEs with missing severity were counted as Severe.
AE	Order	AE_F08	Note:	Incidences were displayed in descending order of frequency of System Organ Class and by Preferred Term within System Organ Class.
AE	Order	AE_F09	Note:	Incidences were displayed in descending order of frequency of Preferred Term.
AE	Dictionary	AE_F14	Note:	System Organ Class and Preferred Term were based on the Version 23.1 of the MedDRA coding dictionary.
AE	Dictionary	AE_F14a	Note:	Preferred Term was based on the Version 23.1 of the MedDRA coding dictionary.
AE	Interval	AE_F15	Note:	Time intervals were determined by the start day of the adverse event.
AE	Count	AE_F16	Note:	n represents the number of subjects that experienced an adverse event in a given category. m represents the number of adverse events in a given category.

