**Notes:**

- 1) Include questions that contribute to the respiratory domain score.
- 2) Include all visits (Baseline and Days 36, 43, 57, 85, 113, 197, 281, 365).

Footnotes

Data Type	Footnote Type	Code	Prefix	Footnote
DS	Study day	DS_L01	[1]	Study day of last dose of study drug was defined as treatment end date - treatment start date + 1.
DS	Study day	DS_L02	[2]	Study day was defined as date of completion or early termination - treatment start date + 1.
DM	Derivation	DM_L01	[1]	Age is calculated by (date of informed consent - date of birth)/365.25, rounded down to the next largest integer using the floor function, in years.
DM	Abbreviation	DM_L02		CFTR = cystic fibrosis transmembrane conductance regulator.
EX	Schedule	EX_L01	Note:	For the 4 mg dose group, 1 medication chamber was expected. For the 8 mg dose group, 2 medication chambers were expected. For the 12 mg dose group, 3 medication chambers were expected. For the 16 mg dose group, 4 medication chambers were expected. For the 20 mg dose group, 5 medication chambers were expected. For the 24 mg dose group, 6 medication chambers were expected.
EX	Derivation	EX_L02	Note:	A medication chamber was counted as completed if nebulization was marked as completed and there was no excess residual in the medication chamber. The medication chamber is the cup recorded on the investigational product administration case report form page.
EX	Count	EX_F01	Note:	Full dose refers to completion of all nebulizers as planned; partial dose refers to incomplete nebulization. Full and partial dose are independent of the presence or absence of excess residual in the medication chamber.
AE	Study day	AE_L01	Note:	Start day and end day of AEs were defined relative to the date of first dose of study drug.
AE	Derivation	AE_L02	Note:	AE Duration (days) was calculated as AE end date - AE start date + 1. Imputed AE start dates and imputed AE end dates were used in the case of partially missing dates. Any duration calculation that required use of imputed AE start date or imputed AE end date were identified by '*'.
AE	Dictionary	AE_L03	Note:	System Organ Class and Preferred Term are based on the Version 23.1 of the MedDRA coding dictionary.
AE	Definition	AE_L04	Note:	All adverse events that occurred within the 24 hours after completion of nebulization for subjects that had an adverse event of pyrexia within the 24 hours after completion of nebulization are listed.

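### SAP 9.3 gives no route to TEAE status for an AE on the first-dose date without a start time, and pooled shell 14.3.1.4 omits the subject counts SAP 9.3.2 calls for

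*SAP*

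**What the plan says.** **TEAE rule.** SAP 9.3 defines TEAEs in general as events that are new or worse once treatment has begun. It then gives three operational routes: a start after the treatment start date; a start on that date "with a time that is equal to or after treatment start time, or that have a missing AE start date"; the last words of that quote are the third route.

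**Date imputation.** SAP 9.1 allows no imputation of safety data except for partial dates, "which will be imputed only for defining TEAEs and for the calculation of the duration of the AE". It has no rule for a missing time. Two exceptions concern AEs that ended on or after the first dose or have no end date. For a month-only start in the first-dose month, "in which case the start day will be set to the first day of first dose of study drug". For a year-only start in the first-dose year, "in which case the start day and month will be set to that of the date of first dose of study drug". Other partial starts default to the first of the month or January 1. SAP 9.1 adds that "any AE with a completely missing date will be classified as a TEAE".

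**Intervals and duration.** SAP 9.3 says "Any TEAE with a completely missing start date will not be categorized into a specific time interval". Table footnote AE_F15 says "Time intervals were determined by the start day of the adverse event". Listing footnote AE_L02 says of duration: "Imputed AE start dates and imputed AE end dates were used in the case of partially missing dates".

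**Counting.** SAP 9.3.2 applies subject-level and event-level counting to the preferred-term summaries, and asks for that summary for the whole study by pooled treatment group. Shell 14.3.1.4, which implements the pooled version, has an Events column for each pooled arm and no n (%); its note 4 asks for event counts. Shells 14.3.1.3 and 14.3.1.3.1 are laid out the same way for each part. All of them carry footnote AE_F19, which describes N as the subjects who had an AE. Note 2 of shell 14.3.1.4 describes N as the subjects at risk.

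**The concern.** The two SAP 9.1 exceptions exist to give doubtful starts TEAE status. Under SAP 9.3 as worded, the date they assign is the one date on which a start time is also required, and none is supplied. An AE known to have started in the first-dose month would be left out, while an AE with no date information is counted. That runs against the SAP's conservative handling elsewhere: missing severity counts as Severe (AE_F07) and missing relationship as Related (AE_F06a). TEAE type, frequency and severity are part of the primary endpoint (SAP 2.2.1), so the choice should not be left to the programmer.

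The pooled table is the only planned display that sets all active against all placebo subjects by preferred term across all TEAEs. Event counts cannot separate one subject with repeated events from several subjects with one each, and the arms differ threefold in size.

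**Working it through.** **1. Apply SAP 9.1, then SAP 9.3.** Assume a first dose on 16 March 2020 at 10:00, for illustration.

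| AE start as recorded | Start date after SAP 9.1 | SAP 9.3 as written | With the added sentence |
|---|---|---|---|
| 16 March, 11:00 | 16 March | TEAE | TEAE |
| 16 March, 09:00 | 16 March | not TEAE | not TEAE |
| 16 March, no time | 16 March | not captured | TEAE |
| March 2020; end missing or 2 April | 16 March | not captured | TEAE |
| March 2020; end 10 March | 1 March | not TEAE | not TEAE |
| 2020 only; end missing or 1 June | 16 March | not captured | TEAE |
| April 2020 | 1 April | TEAE | TEAE |
| no date | none | TEAE | TEAE |

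If the first dose falls on the 1st of a month, a month-only start in that month does not enter the exception, because the 1st is not before the first dose. The default then gives the first-dose date, again with no time. The same holds for a year-only start when the first dose is on January 1.

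**2. All first-dose dates.** Over the 365 dates of a non-leap year, with no end date and no start time, SAP 9.3 gives TEAE status for: earlier month 0, same month 0, later month 365; earlier year 0, same year 0, later year 365. Only same month and same year miss the evident intent. With the added sentence both become 365 and the other four do not change.

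**3. Conditional illustration for month-only starts.** Assume first doses spread evenly over the year and uniform onset. Days from first dose to the end of its month, summed over 365 dates, are 5738 (mean 5738/365 = 15.7). For Part A, capping at 29 days removes 25, leaving 5713.
- Part A, Days 1–29: 5713/(365 × 29) = 54.0%
- Part B, Days 1–57: 5738/(365 × 57) = 27.6%
- Part D, Days 1–32: 5738/(365 × 32) = 49.1%

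These include first doses on the 1st, which reach the first-dose date by the default rule. Without them (5713 − 347 = 5366; 5738 − 365 = 5373) the shares are 5366/10585 = 50.7%, 5373/20805 = 25.8% and 5373/11680 = 46.0%. All are shares of onset days for an AE that already has a month-only start.

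**4. Pooled table.** Planned subjects: active 12 + 12 + 6 = 30; placebo 4 + 4 + 2 = 10. Equal per-subject event rates would print as 3:1. A printed 5 versus 5 events could be:
- 1/30 versus 5/10 subjects: 3.3% − 50.0% = −46.7 points
- 5/30 versus 1/10 subjects: 16.7% − 10.0% = +6.7 points

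**5. Other pooled tables.** 14.3.1.1.2 gives subject counts but no preferred terms. 14.3.2.5 and 14.3.2.7 cover febrile and hypersensitivity reactions only. 14.3.1.2 gives subjects and events by preferred term, but for Parts A, B and D separately.

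**The case against.** **Silence is not exclusion.** SAP 9.3 lists what will be classed as treatment-emergent and does not say that everything else is not. The purpose of the imputation is plain, and a sensible programmer would probably count these AEs. That stands: a reader might infer that the SAP rules them out, and it does not say so. What remains is that no stated route admits them. The third route cannot be stretched to cover partial dates, since that would make the start-date imputation redundant.

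**Few AEs will be affected.** AEs are collected repeatedly on dosing days and at frequent visits and calls afterwards, and the AE listings carry start times. This stands. The percentages in step 3 might be read as the share of TEAEs lost; they are not, because they apply only to AEs that already have a partial date.

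**The pooled information is not lost.** Subject counts can be obtained by adding 14.3.1.2 across parts, which has matching Day 29, 57 and 32 intervals. Subjects take part in only one part, so the sums are valid. Febrile reactions, the known signal, have their own pooled subject counts in 14.3.2.5. This also stands. It limits the point to a mismatch between text and shell, and the 5-versus-5 case is hypothetical.

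**Conclusion.** Both points hold in limited form and are worth correcting before the outputs are run.

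On a literal reading, SAP 9.3 does not capture an AE dated, or imputed, to the first-dose date without a start time. This covers fully dated Day 1 AEs with no time, the two SAP 9.1 exceptions, and the default rule when the first dose is on the 1st of the month or January 1. It does not follow that the imputation fails in general: earlier and later months and years classify as intended, and the duration calculation is unaffected. The number of AEs involved cannot be had from the documents and is probably small.

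Shell 14.3.1.4 does not deliver the subject-level counts in SAP 9.3.2, and no other pooled table gives them by preferred term across all TEAEs. The by-part shells 14.3.1.3 and 14.3.1.3.1 share the mismatch, with less consequence because 14.3.1.2 already gives by-part subject counts. AE_F19 is a labelling error only. The figures of 30 and 10 assume planned enrolment with no added or replaced subjects.

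**What to change.** **SAP 9.3.** Add: *AEs dated, or imputed to, the first-dose date with a missing start time are treatment-emergent unless the end date/time precedes the first dose.* The downside is that a few pre-dose Day 1 events may be counted as TEAEs.

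Do not add a blanket rule that AEs with imputed start dates count in the Overall interval only. A treatment-emergent AE known to have started in the first-dose month began by Study Day 31 at the latest. It therefore lies inside the Part B Day 57 and Part D Day 32 windows, and inside the Part A Day 29 window for 347 of 365 first-dose dates. Such a rule would drop it from those tables.

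**Shells.** In 14.3.1.4, print subject n (%) beside the event count, with the safety analysis set as denominator. Do the same in 14.3.1.3 and 14.3.1.3.1 for consistency. Reword AE_F19 in all of these shells so that N is the column denominator, or delete it.

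**Cost.** One SAP sentence, one added statistic per arm in the pooled and by-part preferred-term shells, and one footnote. No new data are needed.
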